### **7.3.2 Consent**

The consent process is described in detail in Section 5.3.1, above.

## **8 ETHICAL AND REGULATORY CONSIDERATIONS**

### **8.1 Assessment and management of risk, and other ethical considerations**

The research involves working with NHS patients. However, it can be considered low risk since it does not involve an intervention of any kind. The study does not involve drugs, placebos or other substances being administered to participants, nor will the study involve invasive, intrusive, or potentially harmful procedures of any kind. Blood or tissue samples will not be obtained from

participants. Study participants will not be vulnerable or unable to give informed consent (e.g., children, or people with learning disabilities). The study is not likely to induce psychological stress or anxiety, or cause harm or negative consequences beyond that experienced in the participants' everyday lives.

If a participant decides to take part, they will be informed in the Participant Information Sheet and during the consent process that they can change their mind at any time by letting one of the research team know. They will also be informed that they do not need to provide a reason for withdrawing from the study. If they withdraw from the study, we will endeavour to exclude their data from the analysis. However, this may not be possible, since participants' contact details will be destroyed at the end of the project. Their interview data will be linked to their contact details via a unique identification number. This means that, once all contact details have been destroyed, it will no longer be possible for their data to be identified in order to exclude it from the analysis. Participants will be informed of this in the Participant Information Sheet.

It is anticipated that interview telephone call will last approximately 20-30 minutes (1-2 minutes for consent, 1-2 minutes for collecting information pertaining to the helpline call, 15-25 minutes for the semi-structured interview, and 1 minute to collect demographic information). Therefore, the study does not involve prolonged or repetitive testing.

We acknowledge that the design of the study, where pharmacy professionals who operate the helpline service will judge whether or not a potential participant meets the study inclusion/exclusion criteria, may cause selection bias. However, this was discussed among the research team, and it was agreed that it would not be ethical to send invitations to callers where this might cause distress. In addition, discussion with potential research sites has made it clear that they would not participate in a study without these exclusion criteria. Therefore, our research question can only be investigated in this way.

Research suggests that 30% of callers to patient medicines helpline services are from carers of patients. We will therefore include both patients and carers of patients who have use a patient medicines helpline service, if they decide to participate in the study. When carers participate in the study, the issue arises as to whether or not the patient they care for also needs to consent if they have capacity, since the carer may disclose information about the patient during the interview. However, the aim of the study is to explore whether the helpline caller's needs were met when they used the helpline service. When interviewing patients, we will collect background information about them, such as demographics, number of prescribed medicines, and morbidities. We will not ask carers for such information about the patient they care for. Therefore, regarding carers, the focus of the interview is upon them and whether, as a helpline caller, their needs were met. The interview schedule for carers is therefore different to the interview schedule for patients. Interviews with carers will be about their experiences of calling the helpline service, and will not directly ask them questions about the patient they care for. However, if during an interview with a carer they do provide information about the patient they care for, this information will be anonymised at the point of transcription.

Since the research will involve interviewing patients about their experiences of using NHS services as a result of potentially serious and life-threatening illness, they may disclose feelings of distress. If this happens, participants will be reassured that there are support services both within the NHS and external to the NHS which are available for them to discuss their situation with and seek support. A list of contact details for such support services has been created so that the interviewer can have this at hand during the interviews.

The consent process will inform participants that if they disclose any thoughts of a suicidal nature or disclose any thoughts of risk of harm to themselves, we will ask the Medicines Information Manager or Chief Pharmacist of the NHS Trust to contact the participants' GP to inform them of this, since the

## Experiences of using NHS patient medicines helplines

hospital will be able to access their GP details. Since this statement is in the consent process, it is therefore the participants' choice as to whether or not they wish to continue and participate in the study. The participant will also be strongly advised at the end of the interview to speak to their GP or call NHS 111 as soon as possible, to let their GP know how they are feeling so that they can manage their care in this respect. If a study participant is actively threatening harm to themselves when contacted, they will be kept on the phone and explained that it is the study protocol that we will endeavour to contact the emergency services for them. We will ask them for their current location, and a nominated person will be asked to contact the emergency services on behalf of the interviewer, so that the interviewer can remain on the phone with the participant. The nominated person will be either one of the three study supervisors or another member of the University of Bath (either a postgraduate researcher or faculty member of staff) who will be 'on call' for each interview, in case such a situation arises (this will be arranged prior to every interview, to ensure that there is always someone 'on call' for the duration of the interview). The interviewer will conduct the interview using a land line at the University of Bath, and will use his mobile phone to get in touch with the nominated person to inform them that their support is needed.

If potential malpractice is reported by a participant during the study, the researcher (MW), who is a PhD student and does not have expertise in Pharmacy Practice, will discuss this with the supervisory team, two of whom are registered pharmacists with experience of practice in a variety of settings, including medicines information. The supervisory team includes the Chief Investigator, [name]. The supervisory team will respond to the identification of malpractice and/or unsafe medicine-related misunderstandings by contacting the Medicines Information Manager or the Chief Pharmacist or Head of Pharmacy of the NHS Trust.

The situation may arise where the patients who are being interviewed may ask the interviewer (MW) for information and advice about their medicines. The interviewer will make it clear that he is not a trained pharmacy professional and does not have the expertise to answer their question, advising them to re-contact the patient medicines helpline or speak with their GP instead.

The situation may also arise where the participant asks for support with dissatisfaction about the NHS Trust or the helpline service. Such participants will be given the contact number for the Patient Advice Liaison Service for their NHS Trust, since this service functions to deal with patient complaints.

The interviews will involve service users describing their understanding of the information and advice provided by the pharmacy professional who dealt with their helpline enquiry. This has ethical implications, since the service user may have misunderstood the information and advice they received, and experience harm or may not receive the full benefit of their medicines as a consequence. However, the PhD researcher (MW) is not a pharmacy professional and therefore does not have the expertise to necessarily notice if a piece of information sounds unusual or potentially harmful (additionally, the pharmacists' account of the helpline call will not be collected for this study, in order to check the service user's account to it). It is also aimed that the analysis will take place once all 30 interviews have been completed, in collaboration with MJ and JS who have expertise within pharmacy practice. At this point, if MJ and JS notice anything which seems odd or potentially harmful, they will decide what action should be taken. However, prior to analysis, if a piece of information is identified by MW which seems odd or potentially harmful, MW will discuss the case with MJ and/or JS. MJ and JS will then decide, based upon the perceived seriousness of it, the appropriate course of action.

The situation may arise where a potential participant is contacted via the telephone for the purpose of being interviewed and it becomes apparent that they do not have capacity at that time to take part in the study. For example, the individual may appear to be intoxicated or may appear to have difficulty remembering their contact with the helpline service. In line with guidelines by the British Psychological

Society and Health Research Authority, potential participants will only be allowed to take part in the study if they have capacity to make the informed decision to consent (113, 139), and if they seem able to meet the requirements of the study (i.e., being able to recount their experiences of using a patient medicines helpline). Otherwise, the individual will be explained that they do not meet our inclusion criteria for participating in the study, they will be thanked for their time and the call will be ended.

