### **5.2.2 Questionnaire pertaining to the helpline call and participants' background**

In order to add context to the semi-structured interviews, the following background data will be collected directly prior to the telephone interviews using data collection forms (one for participants who are patients, and another for participants who are carers):

*Patients:* Name of the NHS Trust which provides the patient medicines helpline service which they used; date they contacted the patient medicines helpline service; whether or not they had previously used the helpline service; patient type (i.e., whether they were an inpatient or an outpatient); approximate number of prescribed medicines currently taken (participants will be provided with the answer options of 0-1, 2-4, 5-9, and 10 or more).

*Carers:* Name of the NHS Trust which provides the patient medicines helpline service which they used; date they contacted the patient medicines helpline service; whether or not they had previously used the helpline service; relationship to patient.

The following background information will not be asked of carers: name of all medications currently prescribed; current morbidities. This was discussed amongst the research team, and it was decided that collecting information about the patient via the carer, would be unethical unless the patient also provides their consent.

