A script has been developed to facilitate the telephone call with service users, and to ensure that the information which participants receive at the start of the call is standardised. At the start of the telephone call, the participant will be asked if they agree for the call to be audio-recorded. Consent to take part in the study will involve MW reading out all consent statements in the consent form over the telephone and asking the participant if they agree to each statement. The consent statements have been informed by the consent preparation guidance of the Health Research Authority (112), and the University of Bath Research Ethics Approval Committee for Health (117). The statements are:

- 1) Please could you confirm that you have received information about the study, that you have had the opportunity to consider the information, ask questions about the study, and have had these answered satisfactorily?
- 2) Do you understand that your participation is voluntary and that you are free to withdraw from the study at any time without giving a reason, without your medical care or legal rights being affected?
- 3) Do you understand that your anonymised data may be retained for at least 10 years in accordance with the University of Bath Research Data Policy, and that it may be shared and used to support other research in the future?
- 4) Do you understand that parts of your interview may be used verbatim in future publications or presentations and that such quotes will be anonymised (i.e., they will not mention you personally)?

5) Do you understand that if you disclose any thoughts or actions of harm to yourself during this interview, that it is our duty to inform the Pharmacy team at the NHS Trust where you received care, so that they can inform your GP?

6) Do you agree to take part in the study?

The consent process will take approximately 5 minutes. The audio recording for the consent process will be separate from the recording for the interview, to ensure that the interview recording, including the file name, can be anonymised. Prior to the interview, participants will also be made aware that the research is independent of the hospital at which they were admitted, thereby encouraging participants to disclose their experiences of the helpline service, whether positive or negative.

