#### **7.1.3 Inclusion criteria of service users**

Individuals who have contacted a patient medicines helpline with the aim of seeking information and/or support regarding medicines (the contact can be via any means of communication other than face-to-face, such as telephone, email, or online webform); participants can include patients of the organisation which hosts the patient medicines helpline, and carers of such a patient (including parents of patients who are under 16 years old); aged 16 years and over; fluent in English; ability and willingness to provide informed consent; and ability, willingness, and availability to conduct a telephone interview within 1 month of having used an NHS Trust's patient medicines helpline service.

Research suggests that approximately 70% of calls to patient medicines helplines are from patients and 30% of calls are from carers (30). Therefore, both patients and carers will be invited to participate in this study.

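### For carers who are not Trust patients, the self-harm consent statement is inaccurate and the protocol specifies no source for their GP details

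*Protocol*

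**What the plan says.** Protocol section 5.3.1 obtains consent by the researcher "reading out all consent statements in the consent form over the telephone", and requires it of all participants. Six statements are listed, with no separate set for carers. Statement 5 tells the listener that, if they disclose thoughts or acts of harm to themselves, "it is our duty to inform the Pharmacy team at the NHS Trust where you received care, so that they can inform your GP".

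Section 8.1 gives the matching procedure for participants in general: "we will ask the Medicines Information Manager or Chief Pharmacist of the NHS Trust to contact" the participant's GP. The reason given is that the "hospital will be able to access their GP details". Section 8.1 adds that, because the statement forms part of consent, going ahead is the participant's own choice.

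Section 7.1.3 admits patients of the Trust that hosts the helpline and also "carers of such a patient (including parents of patients who are under 16 years old". It does not require a carer to be a patient of that Trust.

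Elsewhere the protocol does treat the two groups separately. Section 5.2.2 has two background forms, "one for participants who are patients, and another for participants who are carers", and section 5.2.3 has two interview schedules.

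**The concern.** A route that works through hospital records suits someone the hospital has treated. A parent ringing about a child's medicines, or a spouse ringing about a partner's, may never have been a patient there. Two things follow for such a carer.

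- They are asked to agree to a statement that misdescribes their position, although section 8.1 relies on that statement for informed choice.
- If they disclose thoughts of self-harm that are not an immediate threat, the protocol states no means by which the message would reach their GP.

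What is at stake is one layer of a safeguard, and the accuracy of consent, in a group the protocol expects to recruit. The research question, sampling and thematic analysis are not involved.

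**Working it through.** No figure in the protocol needs reproducing. The check sets the provisions side by side and asks whether each fits each type of participant.

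**1. Who hears statement 5.** Everyone: section 5.3.1 requires consent from all participants and has all the statements read out.

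**2. Who can take part.** Patients of the Trust, and carers of such patients (7.1.3). Carers divide into those who are also Trust patients and those who are not.

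**3. Fit of the route.**

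| Participant | Reference to care received at the Trust (statement 5) | Stated basis for reaching the GP (8.1) |
|---|---|---|
| Patient | Fits | Applies |
| Carer who is also a Trust patient | Fits | Applies |
| Carer who is not a Trust patient | Inaccurate | Assumes a hospital patient |

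**4. Is another source for a carer's GP specified?** I looked in each place where personal details are recorded.

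- Carer background form (5.2.2): Trust name and date of contact, then "whether or not they had previously used the helpline service; relationship to patient". No GP.
- Demographics form (5.2.4): six demographic items plus an email or postal address. No GP.
- Name and contact details (8.8): held by the research team, and not said to include a GP.
- Call log (5.2.5): uses the enquirer's number from the Trust's enquiry system, and is not said to carry a GP.

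None is specified.

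**5. What still works for the third row.**

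- The carer form records which Trust's helpline was used, so the Pharmacy team there can be informed.
- The interviewer has a list of support services (8.1).
- The participant is strongly advised to speak to their GP or NHS 111 (8.1).
- For an active threat the interviewer stays on the line while a nominated person calls the emergency services (8.1).

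The gap is therefore the onward step from the Pharmacy team to the carer's own GP after a non-imminent disclosure.

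**6. Scale.** Section 7.1.3 cites about 30% of calls as coming from carers, and section 7.2.1 plans an initial 30 interviews. If interviews mirrored calls, which is an assumption because section 7.3.1 sets no carer quota, carers = 30 × 0.30 = 9. Let f be the share of those carers who are not Trust patients. The protocol does not give f, so the number hearing an inaccurate statement is 9 × f, from 0 (f = 0) to 9 (f = 1). This counts people who hear the statement, not disclosures. Disclosures are likely to be few, since section 7.1.4 excludes callers for whom taking part would probably be distressing.

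**The case against.** The strongest reply is that section 8.1 does state a basis, for participants generally, and that nothing in the protocol shows what a Trust can look up for a named person who is not its patient. That stands. A reader might infer that the GP step will fail for carers. The documents do not support this. They show only that the stated premise presumes a hospital patient and that no alternative is given.

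A reader might also infer that carers are left without protection. They are not: every other safeguard in section 8.1 covers them, and the commitment in statement 5 to inform the Pharmacy team can be met for them.

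Nor is section 8.1 wrong throughout. It refers simply to the NHS Trust, which suits carers. The reference to having received care appears only in statement 5, and in 8.1 only the clause on GP access is in question.

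Two supporting observations carry little weight. The lack of a GP item on the study forms is not an error in itself, because the protocol leaves the Trust to find the GP. The sentence telling participants that "the research is independent of the hospital at which they were admitted" is also loose for carers, but it is loose for outpatients too, and it concerns the study's independence and not safeguarding.

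The telephone script is not part of the protocol text and might contain a carer wording. The protocol does not mention one.

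**Conclusion.** The point holds as a minor defect of safety procedure and consent wording. For carers who are not Trust patients, statement 5 is inaccurate, the reason given for expecting the GP to be reached assumes a hospital patient, and no other source for the GP is specified. This is more than missing detail: a stated rule rests on a premise that does not fit an eligible and expected subgroup, so following it as written could leave that carer's GP uninformed.

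The size in disclosures cannot be given from the protocol and is likely small. The conclusion assumes that some participating carers are not Trust patients, which the eligibility criteria allow, and that the consent statements are read as listed. There is no effect on the design, analysis or conclusions.

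**What to change.** 1. Add a carer version of statement 5. It should name the Trust whose helpline the carer contacted and say that their GP will be informed using details the carer provides.
2. Ask carers for their GP practice and for permission to contact it. Asking during the consent call means the detail is in hand before the interview. Asking only if a disclosure occurs holds less personal data, but depends on the carer giving it at that moment. Either way, store and destroy it with the contact details under section 8.8.
3. Amend section 8.1 so that hospital look-up of GP details applies to patients, and the practice supplied by the carer is used for carers. The route through the Trust's pharmacy lead can stay; direct contact by the supervisory team is not needed.

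The cost is one alternative consent wording, one question and one clause in 8.1. The downside is one more personal detail held for some or all carers, for an event expected to be rare, plus an amendment under section 8.4 that also updates the Participant Information Sheet if needed.

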## **8.2 Research Ethics Committee (REC) and other Regulatory review & reports**

This study involves interviewing patients and carers about their experiences of using an NHS service (patient medicines helplines). Therefore, before the start of the study, a favourable opinion will be sought from an NHS REC for the study protocol and all other study documents (e.g., data collection tools).

Any substantial amendments will not be implemented unless the amendment has been reviewed by NHS REC.

All correspondence with the REC will be retained.

The Chief Investigator will be responsible for producing an annual report, and will notify the REC of the end of the study. An annual progress report (APR) will be submitted to the REC within 30 days of the anniversary date on which the favourable opinion was given, and annually until the study is declared ended. If the study is ended prematurely, the Chief Investigator will notify the REC, including the reasons for the premature termination. Within one year after the end of the study, the Chief Investigator will submit a final report with the results, including any publications/abstracts, to the REC.

